8.1.3 Other study parameters

Parameters such as age, sex, relevant history, medication, thyroid history, physical examination, laboratory results (thyrotropin, thyroid hormone levels, serum calcium, parathyroid hormone, glucose, thyroglobulin) and results of additional investigations (extra ultrasonography, FNAC cytology, investigations for coincidental PET-findings, etc.). These will be retrieved by examination of the patient files.

8.2 Pre-inclusion study procedures

8.2.1 Central Cytology Review

It is known that cytological classification of thyroid nodules is highly dependent on both observer and volume (experience), especially when they are classified as being indeterminate. The largest series reported, concluded that secondary cytological review can decrease the indeterminate rate from 38% to 28% [51]. Based on these results, we opt to homogenize our patients by central revision of cytological material by (consensus of) two experienced pathologists based on the Bethesda criteria (Appendix III: The Bethesda System for Reporting Thyroid Cytopathology, §15.3, p91). Based on their final decision, a patient will continue for randomisation in the trial or will be (secondarily) excluded. Besides that, a patient will be

excluded from participation in the trial if any additional diagnostic test (such as for mutation analysis or other additional tests that are not yet part of generally accepted, routine clinical care) were performed on the cytological material prior to inclusion and/or randomization of the patient (during local reading of cytology), as these test results might affect patient management and the patient's/referring physician's willingness to participate in the trial. Furthermore, as all tissue needs to be collected in a tissue-bank for immunohistochemical and genetic analysis, special requirements are needed for tissue collection and storage. These procedures will be described in SOPs (Standard Operating Procedures). As inclusion is based on the cytological result, all tissue from patients in whom a FNAC is performed for a (new) nodule should be collected (and stored) according these requirements, until the point that exclusion is certain (at latest after the central cytology review).

8.2.2 Randomisation, stratification, blinding and treatment allocation

The prognosis of thyroid carcinoma is mainly determined by Metastasis, patient Age, Completeness of resection, local Invasion, and tumour Size (MACIS [52]). Apart from these properties, sensitivity of FDG-PET/CT is mainly determined by nodule size and specificity is mainly deteriorated by follicular origin of the nodule. Only age, nodule size (on ultrasonography), cytological subtype and sex are known at the time of inclusion (Table 4, p48). Recently it was described that lesions larger than 40 mm (T3) carry a higher risk of malignancy compared to smaller lesions (odds ratio: 2.10, 95%-CI: 1.26-3.50) and that men have a higher risk of malignancy than women (odds ratio: 1.51, 95%-CI: 1.20-1.83) [53]. We will use a minimisation strategy [54] to stratify for centre (site) of inclusion, US size, Bethesda subtype, Age and Sex only, meaning that in case patients are homogenously

distributed between both treatment arms over all these four factors, 2:1 randomisation will take place, in all other cases, patients will be allocated to the arm in which this type of patient is underrepresented.

Patients will be randomised in a 2:1 fashion to the experimental and control study arm. Patients, treating physicians, central pathologists and nuclear medicine physicians will be blinded for allocation, however in case of an FDG-PET/CT negative nodule in the experimental study arm, patient and treating physician are unblinded as surgery needs to be cancelled. In all other cases, patients proceed to surgery, but patients and treating physicians are kept blinded with respect allocation of the patient (either FDG-PET/CT positive nodule in the experimental study arm or inclusion in the control study arm regardless of PET-result).

EfFECTS

Factor:	Level 1:	Level 2:	Level 3:	Level 4:
Ultrasonographic	T1a (0-10mm)	T1b (11-20mm)	T2(21-40mm)	≥T3 (>40mm)
Nodule Size:	(13%)	(37%)	(37%)	(13%)
Bethesda Subtype	III (AUS/FLUS)	IV (SFN)		
	(67%)	(33%)		
Age	<45yr (40%)	≥45 yr (60%)		
Sex	Female (80%)	Male (20%)		

 Table 4: Stratification during study including expected fractions (based on [4] and [51]).
 AUS/FLUS: Atypia

 of Undetermined Significance or Follicular Lesion of Undetermined Significance; Rep: repeatedly; SFN: (Suspicious for) Follicular Neoplasm.

8.3 Study procedures

8.3.1 FDG-PET/CT of head and neck

A single FDG-PET/CT of the head and neck without a contrast-enhanced CT is performed in all patients in the local centre according to the EANM guidelines [50], independent of allocation results. The scanned area ranges from meatus acusticus externus to the fossa jugularis sternalis (or down to the lower margin of the arcus aortae in case of retrosternal goitre), with arms down and preferably using a head rest (Figure 3, p49). Only a section of the body is scanned as the possibility that a single (PET-positive) lesion outside the thyroid bed is the only evidence of DTC is extremely rare and decreasing the scan range will decrease the effective dose of the investigation. Most of these findings are supposed to be coincidental findings unrelated to DTC and harbour a very low a posterior probability to be of serious consequences. could be considered as "screening a healthy population using FDG-PET" which is highly controversial and probably will lead to increase use of diagnostics and expenditure of public funds and could demotivate physicians in including patients in such a trial. E.g. findings of a positive lesion in the colon would certainly be unrelated to DTC, might lead to endoscopic examination which are costly, could lead to complications for the patient, have a low probability to lead to a serious medical condition requiring therapy and would finally demotivate the physician to include more patients.

[figure not shown]

Figure 3: Position of the normal thyroid.

As an example guideline, in short: patients are asked to refrain from eating and drinking for 6 hours, only water and medications are allowed. In insulin-dependent diabetics, insulin levels should be as low as possible, while maintaining normoglycemia (serum fasting glucose <200 mg/dL [<11.1 mmol/L]). No (short-acting) insulin may be injected in the 4 hours before FDG-infusion to reach normoglycemia.

At the department of nuclear medicine, patients are prehydrated using 500 mL of tap water orally. An i.v. cannula is placed in a peripheral vein and about 3.45 MBq/ kg (<25% bed overlap) or 1.725 MBq/ kg (50% bed overlap) FDG (based on 3D acquisition, 4 min/bedpost) is injected intravenously after which the cannula can be removed. This administered FDG-dose may be adapted to local standards as long as these do not violate the current EANM guidelines [50, 55]. Adaptation to this those can be performed incorporating factors such as scanner sensitivity, scan speed and bed overlap.

The patient is incubated alone in a supine position for 60 minutes (+/- 5 minutes) in a warmed (thermoneutral) environment and asked to refrain from muscle activity (no talking, etc.). In case of severe claustrophobia, the use of a benzodiazepine (e.g. oxazepam 10 mg) is allowed.

After incubation, the patient is positioned in the scanner using a head rest to prevent motion mismatch between PET and CT. After a scout view (Figure 4, p50) and a low-dose, non-contrast enhanced CT, PET-acquisition of the head and neck is performed for at least 2 min per bed position. Two bed positions are usually enough to cover the range from the meatus acusticus externus to the fossa jugularis sternalis (or down to the lower margin of the arcus aortae in case of retrosternal goitre).

After the PET-acquisition, the scan is complete and the patient can go home without any further restrictions. The total examination takes around 1.5 hours. Images will be reconstructed using the departments own protocol, including corrections for isotope decay, attenuation, scatter,

dead time and are cross-calibrated to the dose-calibrator of the FDG-dose and in conjunction with the EANM guidelines [50, 55]. The reconstructed FDG-PET/CT images must not be reported and are digitally pseudonymised and submitted for central reading. The results of this examination will be withheld from the patients and treating physicians. Patients are eligible for compensation of the travelling expenses.

FDG-PET/CT is an established (and for a number of other indications proven cost-effective) procedure for multiple oncological and non-oncological issues, covered by the Basic Insurance Package. FDG-PET/CT is a relative non-invasive procedure with only minimal risks attached to it (see §13.1.1: FDG-PET/CT, p78). Administration of FDG does not result in any adverse events. An FDG-PET/CT scan is widely available in almost all hospitals in the Netherlands and can usually be performed within 3 working days. A standard operating procedure (SOP) will be available.

The use of different acquisition protocols (for different departments and different PETscanners) causes heterogeneity in image quality. This probably deteriorates the power of this study, but at the same time will improve applicability of the results for clinical practice. The central PET-reading committee of this study has experience with multiple models of PETscanners.

[figure not shown]

Figure 4: Topograms showing the major landmarks: the meatus acusticus externus (*MAE*), the fossa jugularis sternalis (*FJS*) and the lower margin of the arcus aortae (*LAA*).

Definition of positive and negative FDG-PET/CT:

A positive FDG-PET/CT is defined as focal FDG-accumulation at the site of the FNACindeterminate thyroid nodule higher than (thyroid) background. All other cases are considered FDG-PET/CT negative. For example, see Figure 5, p51. In case of diffuse thyroid FDG-uptake (thyroiditis), the same definition is used, but the higher background should be noted.

The treating physician should receive written notification of the consequences of this result (surgery or not) within one week of the FDG-PET/CT. No disclosure of PET-result of the thyroid nodule (positive or negative) or the study arm allocation should be given.

Contralateral incidentalomas:

In case of an extra FDG-PET/CT-positive thyroid lesion *contralateral* to the thyroid nodule under investigation, it is considered an incidentaloma and worked-up accordingly (~35% harbour malignancy [56]) before a *ipsilateral* hemithyroidectomy is performed. This is not necessary in case total thyroidectomy is scheduled.

Relevant coincidental findings:

In case of clinically relevant coincidental findings (e.g. suspicion of a head & neck carcinoma, oesophageal carcinoma, lung carcinoma or (FDG-avid) cervical or mediastinal lymphadenopathy) this should be reported to the treating physician in writing. Cervical lymphadenopathy without focal thyroid uptake needs further work-up (e.g. US+FNAC, MRI).

[figure not shown]

Figure 5: Example of a FDG-PET/CT positive thyroid nodule in the isthmus, which proved to be a 10 mm differentiated papillary thyroid carcinoma (pT1a cN0M0)

8.3.2 Confirmatory Neck US

A confirmatory US of the neck is performed locally by a dedicated head and neck radiologist in all FDG-PET-negative patients in the experimental arm, 12 months after inclusion. No preparations are needed. An ultrasound is performed in supine position after application of conducting gel. If nodule size is stable (i.e., no more than a 50% change in volume or <20% increase in at least two nodule dimensions in solid nodules or in the solid portion of mixed cystic-solid nodules), the interval before the next follow-up clinical examination or US may be longer, e.g., every 3–5 years. If there is evidence for nodule growth either by palpation or on US (more than a 50% change in volume or a 20% increase in at least two nodule dimensions with a minimal increase of 2 mm in solid nodules or in the solid portion of mixed cystic-solid nodules), the FNAC should preferably be repeated (on discretion of the physician performing the US), preferably under US guidance: the neck will be cleaned with alcohol and a fine-needle will be inserted into the lesion, causing no more pain than a regular venapunction. Other indication for FNAC are also on discretion of the physician performing the US, but should take into account prior US results. The patient is treated further according to the guidelines [5, 6]. Afterwards the patient can go home without any further restriction. The total examination takes around 0.5 hours. The results of the confirmatory US are known by the treating physician, PI and the patient is informed (i.e. no blinding). Patients are eligible for compensation of the travelling expenses.

8.3.3 Questionnaires

All study patients will be asked to fill in 6 self-administered questionnaires in their native language at baseline, after 3 months (or directly after surgery+¹³¹I-RIA), after 6 months and after 12 months. Together these 6 questionnaires take about 30-45 min to fill in:

- RAND-36 V2.0 (SF36-II): The RAND-36 V2.0 is a validated translation in Dutch of the Short Form health survey (SF36-II) comprising 36 questions yielding a 9-scale profile of function health, wellbeing and psychometrically based physical and mental health [57]. It takes approximately 5 minutes to complete. As the SF36-II was not originally designed for use in economic evaluations or to determine QALYs, the SF-6D can be created by applying a scoring method, focusing on seven of the eight health domains of the SF36-II [58] (Appendix VII: , §15.7 p98).
- EQ-5D-5L: EuroQol 5-dimensional 5-level questionnaire: indexing health status, 2 pages including a single visual analogue scale (VAS) [59]. It takes approximately 5 minutes to complete (Appendix VII: , §15.7 p98)..

- iPCQ: Productivity Costs Questionnaire, 12 questions on health and losses of productivity in paid and unpaid labour [60]. It takes approximately 5 minutes to complete (Appendix VII: , §15.7 p98).
- iMCQ: Medical Consumption Questionnaire, indexing direct costs of self-reported health care consumption through 35 short questions. It takes a maximum of 20 minutes to complete [61].
- ThyPRO: Thyroid Patient-Reported Outcome, a disease specific 13-scale 84-item questionnaire designed for benign thyroid disease, but being investigated for use in DTC.
 [62] It takes approximately 14 minutes to complete (Appendix VII: , §15.7 p98).
- DT&PL: Distress Thermometer: a 11-point VAS including a 35-item problem list [63]. Based on expert opinion (by dr. [name], endocrinologist at Radboudumc), we will only use the VAS, since the 35-item problem list mostly overlaps with the content of the other questionnaires. The entire DT&PL takes approximately 5-10 minutes to complete. We estimate that the VAS itself will take a maximum of two minutes to complete. (Appendix VII: , §15.7 p98).

Questionnaires are returned to the PI either by mail or email.

8.3.4 Cytology and histopathology analysis

In the study, cytopathology and histopathology specimens are collected. After cytopathology is collected from individual patients during FNA (prior to study inclusion), cytopathology slides are reviewed at the Radboudumc by two experienced thyroid pathologists to ensure appropriate inclusion in the study. If the first and second pathologist disagree, a third dedicated pathologist will be consulted. Consensus upon classification as either Bethesda category III or IV has to be reached before inclusion of a patient into the study (§8.2.1, p46). Cytopathology samples are returned and stored in local tissue banks at the centre where the FNA was initially performed. Before start of the study, a consensus meeting was held with the dedicated pathologists from the different centres to minimise interobserver variation.

After surgery, thyroidectomy specimens are being stored at the hospital where the surgery has been performed and will be collected at the end of the study. After surgery in all appropriate study patients is completed, histopathology specimens will be reviewed at the Radboudumc by the same experienced thyroid pathologists but an expert of the LUMC may be consulted for specific cases. Characteristics of the lesion like type of lesion, size, cell type, inflammation and vascularity will be scored (see §8.1.2, p45) in adherence to the World Health Organization guidelines [64].

Next, cytological and histopathological tissue characteristics will be analysed in relation to FDG-PET/CT findings in order to determine whether specific tissue characteristics can explain false positive or negative FDG-PET/CT results - like for instance high vascularity or cell type.

Definition of malignant and benign thyroid nodules:

A nodule is considered malignant, in case malignancy is diagnosed at the location of the nodule. All other cases are considered benign nodules.

[figure not shown]
Following advanced insights and in accordance with WHO guidelines, pre-malignant entities such as non-invasive follicular thyroid neoplasm with papillary-like nuclear features (NIFTP), follicular tumor of uncertain malignant potential (FT-UMP) and well-differentiated tumor of uncertain malignant potential (WDT-UMP) are distinguished. These are strictly considered benign though potentially precancerous lesions, for which thyroid lobectomy is justified [65, 66].

As such, a FDG-PET/CT scan is considered true positive if the nodule that was FDG-avid harbors any type of histopathology that warrants surgery, including malignancy, NIFTP, FT-UMP and WDT-UMP. If such a nodule is non-FDG-avid, it will be considered false-negative.

In case a DTC microcarcinoma (T1a or diameter ≤10mm) is found within a much larger nodule, this is considered a coincidental finding. The patient will be treated for DTC (in the special case of a papillary unifocal microcarcinoma, according to the guidelines one can suffice with a therapeutic hemithyroidectomy without completing thyroidectomy and ¹³¹I-RIA [5]). In case this much larger nodule was positive on the FDG-PET/CT, it is considered false-positive; in case the nodule was negative on the FDG-PET/CT, it is considered true-negative.

Lesion-by-lesion qualification of thyroid nodules:

Five locations are considered (left/right lobe with upper/lower pole and central: isthmus/lobus pyramidalis: Figure 6, p54). Qualification of the PET result to be true or false is based on anatomically matched locations (e.g. an FDG-PET/CT positive lesion at the location of a malignant nodule is a true-positive result). In case in doubt (e.g. a node centrally in the left or right lobe), consensus reading by pathologist, surgeon and nuclear medicine physician Figure 6: Anatomy and subdivision of the will be performed.

normal thyroid gland

Multifocality:

In case the patient receives surgery for a FDG-negative nodule (only in the control arm) but this nodule is found to contain malignant tissue, the patient is considered false-negative.

If, however, in the same patient a second malignant nodule is found in the contralateral thyroid lobe at completion thyroidectomy, which was positive on PET ("true-positive"), the patient is considered false-negative and thus the treatment following the PET-scan unbeneficial.

The reason for this is that it was not the FDG-PET/CT-scan that proved the indication for diagnostic surgery, as the lesion under investigation was considered negative, even though the patient is diagnosed correctly with DTC at surgery. In other words: if the patient would have been included in the experimental study arm, the false-negative lesion would have led to a follow-up policy and the contralateral malignancy would never have been diagnosed by a hemithyroidectomy of the site of the false-positive lesion (unless the work-up for a contralateral incidentaloma would have let to a true-positive result).

As stated before, PET-incidentalomas must be worked-up before surgery unless total thyroidectomy is planned as the initial procedure. Abovementioned rare case could therefore only occur if the contralateral PET-incidentaloma was found benign/unsuspicious at work-up or initial total thyroidectomy was planned.

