1.5 Concerns and shortcomings

Recently, Deandreis et al. [20] described 55 patients scheduled for surgery of FNACindeterminate thyroid nodules. Of the nodules, 61% was benign and 18% definitely malignant. The remaining 21% was of uncertain malignant potential. They described a positive and negative predictive value of 57% and 81% respectively for definite and uncertain malignant TNs. They reported 5 FDG-PET/CT false negative lesions (3 tumours of uncertain malignant potential, 2 papillary carcinomas of 10 and 20mm) and they explain the discordance of their findings compared to other publications, by suggesting that it may be related to the definition of "indeterminate cytology" itself or to the heterogeneity of the pathology itself (small and/or well-differentiated tumours show limited FDG-uptake). There is an exceptionally large fraction of lesions with uncertain malignant potential and it can be debated whether these lesions should have been qualified as benign or malignant. The authors chose the latter, but a negative predictive value of 92% can be computed when these lesions of uncertain malignant potential are considered benign, which is much more concordant with previous reports in literature. Twenty-five of 55 scans (45%) were FDG-PET/CT negative, comparable to our meta-analysis (37%).

False-positivity, or a poor positive predictive value, may also be a concern, as these patients still undergo unbeneficial surgery. The only independent predictive factor for FDG-uptake was cellular atypia (present in both benign and malignant nodules). Current literature mainly focuses on FDG-uptake in known thyroid carcinoma [21-24] or (in vitro) in thyroid cells [25], therefore the limited specificity of FDG-PET/CT for (FNAC-indeterminate) thyroid nodules is still poorly understood. Whether previously described diagnostic tests (e.g. immunohistochemistry, gene expression classification) show complementary or additional value needs to be determined.

To our knowledge no studies have been performed to investigate the effect of a wait-and-see policy in patients with a very low probability of malignancy in cytological indeterminate nodules. The effects on HRQoL and costs are only modelled and not prospectively evaluated.

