8. METHODS

8.1 Study parameters/endpoints

8.1.1 Main study parameter/endpoint

The fraction of unbeneficial treatment (i.e. surgery in benign disease plus watchful waiting in malignant disease) in both study arms based on intention-to-treat.

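### Sections 8.1.1 and 8.3.4 score NIFTP, FT-UMP and WDT-UMP nodules in opposite ways, so the primary result depends on which text is followed

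*Protocol*

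**What the plan says.** Section 8.1.1 defines the endpoint: "The fraction of unbeneficial treatment (i.e. surgery in benign disease plus watchful waiting in malignant disease) in both study arms based on intention-to-treat".

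Section 8.3.4 gives the histological rule: "A nodule is considered malignant, in case malignancy is diagnosed at the location of the nodule. All other cases are considered benign nodules". It then takes up NIFTP, FT-UMP and WDT-UMP: "These are strictly considered benign though potentially precancerous lesions, for which thyroid lobectomy is justified". Next it turns to the scan, which is "considered true positive if the nodule that was FDG-avid harbors any type of histopathology that warrants surgery", and it lists these three entities beside malignancy. A non-avid nodule of the same kind is false negative.

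Section 4.4 plans with a control rate of 73.1% (136 of 186 benign lesions above 10 mm). The experimental rate is 40.3% (75 of 186 lesions that are false positive or false negative).

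The multifocality paragraph of 8.3.4 deals with a control patient operated on for a PET-negative nodule that proves malignant, with a second, PET-positive cancer in the other lobe: "the patient is considered false-negative and thus the treatment following the PET-scan unbeneficial".

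**The concern.** For these three entities the protocol gives two answers. Under 8.1.1 with the benign label, operating is an unbeneficial event and watchful waiting is not. Under the true/false-positive scoring it is the reverse. No section says which class feeds the primary endpoint.

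In the control arm everyone is operated on, so the endpoint is simply the benign fraction. In the experimental arm it is false positives plus false negatives, as 4.4 computes it. The two counts are compatible only if both use the same meaning of disease. Followed literally, controls could be scored with these lesions as benign and the experimental arm with them as disease.

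The multifocality sentence is a second, smaller conflict. Surgery for malignancy is not unbeneficial under 8.1.1, whatever the scan showed. The protocol defends the score by what would have happened had the patient been in the other arm, which is not that patient's outcome under intention-to-treat. Section 8.3.4 places the situation only in the control arm, so it can only raise the control rate.

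If the choice stays open, it could be made once histology is known.

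**Working it through.** **The plan's own figure.** Inputs from 4.4: control 136/186 = 73.1%, experimental 75/186 = 40.3%, difference 32.8 points, 60 + 30 analysable, one-tailed alpha 0.025. Exact enumeration of the one-sided Fisher test gives power 0.801, so the stated 90 patients at 0.80 reproduces.

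**Assumptions.** Let q be the share of all nodules that are NIFTP, FT-UMP or WDT-UMP, and s the fraction of those that are FDG-avid. The protocol gives neither for this population. I use q = 5% and 10%, and s = 55% and 75%. The lower s is about 75/136, roughly the PET-positive rate that 4.4 implies for benign lesions. The only related figure is one cited series in 1.5 ("The remaining 21% was of uncertain malignant potential"), a share that the protocol itself calls exceptionally large.

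**Moving these lesions from benign to disease, in both arms:**
- Control rate falls by q.
- Experimental rate loses q·s (avid, no longer false positive) and gains q·(1−s) (non-avid, now false negative).
- The difference therefore falls by 2q(1−s).

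Moving them from malignant in planning to benign now reverses every sign, so the difference rises by 2q(1−s).

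| q | s | Benign in planning, disease now | Power | Malignant in planning, benign now | Power |
|---|---|---|---|---|---|
| 5% | 75% | 68.1% vs 37.8%, 30.3 points | 0.72 | 78.1% vs 42.8%, 35.3 points | 0.87 |
| 5% | 55% | 68.1% vs 39.8%, 28.3 points | 0.66 | 78.1% vs 40.8%, 37.3 points | 0.91 |
| 10% | 75% | 63.1% vs 35.3%, 27.8 points | 0.64 | 83.1% vs 45.3%, 37.8 points | 0.93 |
| 10% | 55% | 63.1% vs 39.3%, 23.8 points | 0.49 | 83.1% vs 41.3%, 41.8 points | 0.97 |

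(Control rate first. Power by the same exact enumeration.) If the definition matches the one used in planning, nothing moves and power stays at 0.80.

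**Mixed scoring.** Take q = 5%, s = 75%, with the lesions benign in planning. Controls scored by the benign label stay at 73.1%. The experimental arm scored by false positives plus false negatives is 40.3 − 3.75 + 1.25 = 37.8%. The difference becomes 35.3 points, against 32.8 (benign in both arms) or 30.3 (disease in both arms). The extra points come only from using two definitions.

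**Ascertainment.** Under the broad definition, the q·(1−s) = 1.25 points of non-avid lesions in the experimental arm belong to patients who are not operated on. They get ultrasound, with cytology on indication (8.3.2), whereas 8.3.4 identifies these entities by histopathology. If all are missed, the experimental rate is 36.6% and the difference 31.5 points rather than 30.3.

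**Multifocality.** Each control so scored adds 1/44 = 2.3 points, or 1/30 = 3.3 points of analysable controls. For frequency, the protocol's false-negative share of 3/225 gives 44 × 3/225 = 0.6 PET-negative control cancers, before requiring a PET-positive contralateral cancer as well.

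**Safety rules.** Sections 8.7 and 8.4.1 act at 4 of 22 and 6 of 44 false negatives, tested against 5%. If non-avid lesions of this kind are added to the expected 1.3%, the rate is 1.3 + 1.25 = about 2.6% (q = 5%, s = 75%) or 1.3 + 4.5 = 5.8% (q = 10%, s = 55%). The second lies above the accepted 5%.

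**The case against.** The best defence is that two constructs are being mixed. Section 8.1.1 scores treatment by benign or malignant disease, 8.3.4 says plainly that these lesions are benign, and the true/false-positive paragraph is about the scan, a secondary parameter. On that reading the endpoint is determined. This does not remove the conflict, because the protocol itself carries scan scoring into the primary endpoint. Section 4.4 builds the experimental rate from false positives and false negatives, and the multifocality sentence goes directly from false negative to unbeneficial.

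Other parts of the defence stand.

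- A reader might infer that the broad definition necessarily costs power. The documents do not support that. The planning studies date from 2003 to 2010 (Appendix IV), and the reference list includes a guideline review whose title presents NIFTP as a renaming of a non-invasive carcinoma variant. Such lesions may already sit among the malignant cases behind 4.4, and how uncertain-potential lesions were classed there is not shown.
- A reader might take the 21% in 1.5 as the expected share. It comes from one series that the protocol calls unusual, and it does not mention NIFTP.
- A reader might infer that every PET-negative control cancer is scored unbeneficial. The word is attached only to the contralateral case, which 8.3.4 calls rare. The plain case is called false negative and no more.
- Central pathologists are blinded to allocation (8.2.2), which limits the scope for a choice informed by results, and an analysis plan not at hand may settle the point. The contradiction would still stand in the protocol.

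**Conclusion.** The contradiction is real and touches the primary endpoint: the same nodule is benign in one place and disease in another, and the link from scan scoring to unbeneficial treatment is made by the protocol's own text. Its size is not known. Across the assumed shares and avidities the contrast runs from 23.8 to 41.8 points against the planned 32.8, and it can move either way. At 5% and 75%, power is about 0.72 or about 0.87 instead of 0.80. These figures illustrate sensitivity to the definition and do not predict a loss.

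The multifocality score contradicts 8.1.1 and can only favour PET, but few if any patients should meet it. It should be corrected for consistency, and it is not evidence of a material bias.

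**What to change.** Before allocation and histology are merged:

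- Reconcile 8.1.1, 8.3.4 and 4.4 so that one stated disease definition scores the primary endpoint identically in both arms. Report the other as a named sensitivity analysis.
- If the broad definition is primary, state that non-avid lesions in unoperated experimental-arm patients are mostly not ascertained histologically, and say how they are counted.
- Keep PET-accuracy scoring separate from the endpoint. Restrict the multifocality sentence to accuracy by deleting, for control patients, its closing clause that calls the treatment unbeneficial.
- State which definition feeds the 4/22 and 6/44 rules. The safety committee section records that the interim analysis took place in April 2018, so for 4/22 this means documenting what was used.

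The cost is a short amendment and one extra analysis. The expected effect may shift in either direction.
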